1.0 Background

Rotator cuff tears are currently one of the most common causes of musculoskeletal pain and disability, and affect between 30% and 50% of the adult population over the age of 50 years.^{16,17} A torn rotator cuff can cause progressive loss of shoulder function and significant pain.^{4,5} The ramifications of rotator cuff tears are realized at both the individual and societal level where the direct costs of diagnosis and treatment and the indirect costs of loss of income, missed workdays, and disability payments continue to rise at exponential rates.^{17,18} The rate at which arthroscopic rotator cuff repair is being performed has increased by greater than 500% over the last 15 years.^{18,19} Given these high personal and societal costs, it is paramount to improve rotator cuff healing rates and decrease re-tearing and the need for reoperation.

Significant advancements in arthroscopic surgical techniques have led to a more stable mechanical environment to promote rotator cuff healing following repair.²⁰ Despite these major technical advances, there has been relatively slow progress consistently improving the biologic environment of healing tissues. This is especially true for rotator cuff repair where incomplete healing and re-tears remain a common postoperative complication. Studies suggest re-tear rates of up to 40% following small and medium tear repairs, and as high as 94% following for large and chronic tear repairs.^{21,22} Failure to heal the rotator cuff and rotator cuff re-tearing have clinical ramifications aside from the aforementioned societal and financial implications. Longitudinal clinical studies have demonstrated decreased functional improvement, diminished clinical outcomes, and lower patient satisfaction in those that have failure of healing or re-tears following rotator cuff repair.^{4,5}

There are many predisposing factors that may prompt rotator cuff healing failure or re-tear. These factors can be divided into patient-specific factors (patient age, gender, body-mass index (BMI), smoking status, and comorbidities) and tear-specific factors (tear pattern, tear size, and tear chronicity).^{23,24} The major biologic sequelae of a constellation of both patient- and tear-specific factors are the changes to the muscle-tendon unit.^{7,25} The hallmarks of these changes are muscle atrophy, fatty infiltration, and intercellular fibrosis of the torn rotator cuff muscle-tendon unit.^{7,25} These changes begin at the time of the tear and currently go largely unaddressed at the time of repair.

Researchers have pursued biologic augmentation at the time of arthroscopic rotator cuff repair; however, time-zero modifications to the healing interface with growth factors, platelet-rich plasma, and stem cells have failed to address the hallmarks of the biologic problem (muscle atrophy, fatty infiltration, and intercellular fibrosis).²⁶ Therefore, these modalities in both preclinical and clinical models have failed to consistently demonstrate improvements in healing rates, re-tear rates, functional results, or patient satisfaction.²⁷⁻²⁹ Recently, researchers have attempted to address the biologic hallmarks of rotator cuff tearing with a series of animal studies examining the effects of anabolic steroids on rotator cuff healing.^{25,30,31} This line of preclinical studies demonstrated that anabolic steroids, when administered as an adjuvant to rotator cuff repair, can halt the progression of fatty infiltration, decrease muscle atrophy, and promote rotator cuff healing.

Despite the wide range of doses in controlled clinical trials, our proposed dose has not been studied. The drug manufacturer, Gemini Labs LLC, is providing the drug in 6mg doses for the study and the proposed oxandrolone dose in men is 24mg/day. Currently, the FDA-approved dose in adults is up to 20mg/day, usually in two to four divided doses. Most controlled studies use doses of 5–20mg/day.^{3,36} In patients with moderate to severe alcoholic hepatitis, however, doses have been given up to 80mg/day.³⁷ Adverse events are typically dose-dependent and correlate to the duration of use.³⁶ Serious hepatic toxicity has not been shown with short term (≤ 3 months) treatment of oxandrolone, even with up to 80mg/day.^{36,37}

The objective of this research proposal is to perform a clinical trial, translating this previous line of preclinical research into the clinical arena. The purpose of this double-blind, randomized study is to compare the outcomes of rotator cuff repair augmented with 12 weeks of an oral, FDA-approved anabolic steroid to the outcomes of rotator cuff repair augmented with 12 weeks of placebo medication. The long-term implications of this study has the potential to provide direct and immediate clinical impact and healthcare savings by aiding rotator cuff healing.

2.0 Objectives and Purpose

Specific Aim #1. Determine if oral Oxandrolone administration will improve rotator cuff healing following rotator cuff repair.

Oxandrolone is an orally administered synthetic derivative of testosterone that is approved by the Federal Drug Administration (FDA) in patients who have lost weight resulting from extensive surgery, severe trauma, chronic infection, or as an adjunctive therapy to promote weight gain. It is also approved for bone pain associated with osteoporosis, and to attenuate protein catabolism associated with the prolonged use of corticosteroids. Oral administration of Oxandrolone has demonstrated increases in lean mass, protein synthesis, and wound healing with no long-term adverse events in trauma patients as well as healthy male controls.¹⁻³ The aforementioned safety and efficacy profile of oral Oxandrolone makes it an appealing adjuvant treatment to counteract the major biologic consequences of a chronically torn rotator cuff (muscle atrophy, fatty infiltration, and intercellular fibrosis), which are known to lead to poor healing and diminished clinical outcomes.^{4,5} The primary aim of this double-blind, randomized study is to compare the rotator cuff healing rates between an experimental group receiving 12 weeks of daily, orally administered Oxandrolone following rotator cuff repair to a control group undergoing the same rotator cuff repair and receiving 12 weeks of a daily, orally administered placebo medication. The healing spectrum from complete healing to re-tear will be defined based on a previously validated diagnostic imaging metric. The primary outcome measure is rotator cuff muscle-tendon structural healing as measured by the Sugaya classification on magnetic resonance imaging (MRI) at the primary end-point of 6 months.⁶ We will continue to follow for one year. We hypothesize that those in the experimental group (Oxandrolone group) will have greater rotator cuff tendon structural healing as compared to the control (Placebo group) at the primary end-point of 6 months post-operative.

The secondary measure of healing will be the degree of fatty infiltration of the muscle-tendon unit on MRI using the Goutallier grading classification.⁷ We hypothesize that those in the experimental group (Oxandrolone group) will have less fatty infiltrate as compared to the control (Placebo group) at primary end-point of 1 year.

Specific Aim #2. To determine if oral Oxandrolone administration will improve shoulder functional outcomes following rotator cuff repair.

Multiple rotator cuff repair studies have demonstrated that patients with MRI evidence of rotator cuff muscle-tendon healing following repair have improved function in the form of postoperative range of motion and strength.^{8,9} The secondary aim of this double-blind, randomized study is to compare the functional outcomes between the experimental group (rotator cuff repair and 12 weeks of Oxandrolone) and the control group (rotator cuff repair and 12 weeks of placebo). Functional outcome will be defined based on the literature standards of postoperative shoulder active range of motion and isometric strength.^{10,11} We hypothesize that those in the experimental group will have improved shoulder functional outcomes following rotator cuff repair compared to the placebo group at 1 year. .

Specific Aim #3: To determine if Oxandrolone administration will improve patient-reported outcomes (PROs) and patient satisfaction following rotator cuff repair.

Rotator cuff muscle-tendon healing following repair is also associated with improved patient-reported outcomes (PROs) and patient satisfaction.^{8,9} The third aim of this double-blind, randomized study is to compare the PROs and satisfaction level between the experimental group (rotator cuff repair and 12 weeks of Oxandrolone) and the control group (rotator cuff repair and 12 weeks of placebo). Patient-reported outcome will be defined based on the validated American Shoulder and Elbow Surgeons Shoulder Assessment (ASES) and a Visual Analog Pain Scale (VAS).¹¹⁻¹³ Patient satisfaction will be assessed with the literature standard, single-stem patient acceptable symptom state (PASS)

questionnaire.^{11,14,15} We hypothesize that the experimental group will have improved patient-reported outcomes and satisfaction compared to the placebo group at 1 year.

3.0 Study Design

Trial Design

This is a single-center, prospective 1:1 double blind randomized control trial. The trial will be conducted at the University of Southern California (USC), Keck School of Medicine in Los Angeles, California. Patients will be recruited from the Department of Orthopaedics. Men and women, 40–75 years of age, with MRI proven rotator cuff tears, indicated and scheduled for repair will be eligible for inclusion. Men and women with acute tears and those with significant comorbid liver, lung, cardiac, and kidney conditions will be excluded. Women who are pregnant or nursing will also be excluded. Women of child-bearing potential will be required to take a monthly urine pregnancy test and be on an agreed upon contraceptive. Participants will be randomized into one of two groups, a control group (receiving placebo medication) and an experimental group (receiving oral Oxandrolone, 12 mg twice daily for men and 6 mg twice daily for women for 12 weeks). Dosing will begin at the time of surgery and continue for 12 weeks, with medication dispensed by the USC Pharmacy. The study will be double-blinded: neither the treating surgeon nor the patient will know to which group the patient is enrolled.

Surgical Procedure

Arthroscopic inspection of the shoulder will be performed to verify the presence of a rotator cuff tear and to measure the size of the tear. In all cases a standard arthroscopic double-row technique will be used to repair the rotator cuff tendon.^{19,20} Treatment of the biceps tendon, need for subacromial decompression, and/or acromioclavicular joint resection will be at each surgeon's discretion. Intraoperative measurements of rotator cuff tear type and size as well as the details of the surgical procedure will be recorded.

Postoperative Rehabilitation

All participants in the study will undergo a standardized rehabilitation protocol for rotator cuff repair as agreed upon by the surgeons involved. Rehabilitation will be supervised by a licensed physical therapist. Adherence to the rehabilitation protocol will be assessed by review of patient treatment logs. If there are alterations to the standard postoperative rehabilitation course, the treating surgeon will be notified and will determine if the alteration in course warrants removal from the study. Patients who do not meet 80% adherence to the standardized protocol will be considered non-compliant and controlled for in the data analysis.

Feasibility

The study team has the experience, knowledge, and capability to conduct this study. The surgeons involved perform approximately 400 rotator cuff repairs per year. The study team assembled has conducted similar prospective studies in the past on rotator cuff healing. In addition, the study team has experience with clinical trials involving anabolic steroids.

The collaborative nature of the study is exemplified in the sharing of responsibilities. The majority of the clinical care proposed in this study (demographic data, medical history, physical examinations, vital signs, preoperative MRI without contrast) is standard-of-care treatment for rotator cuff tears all surgeons involved and will be overseen as such. The outcome measures collection will be monitored by a research coordinator through the Department of Orthopaedic Surgery. The research coordinator will be responsible for arranging follow-up care and confirming that postoperative MRI, functional tests, and patient-reported outcome measure are completed. The safety profile including laboratory tests and body composition will be performed under the guidance and monitoring of [name] based on his extensive knowledge of the anabolic steroid field. The body composition measurements will be made in [name]

Protocol Number: APP-17-01020

Version Date: 9/1/2017

laboratory. Postoperative rotator cuff repair rehabilitation and patient-reported outcome data will be overseen by [name], given her career-long expertise in shoulder-specific rehabilitation and shoulder pathology patient-reported outcome measures. In addition, patient recruitment will not be an issue as the study-eligible population significantly overlaps with the patient population most frequently affected by symptomatic, chronic rotator cuff tears.

Key Personnel

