5.0 Selection and Randomization of Subjects

Participants

Men and women, aged 40-75 years, presenting to an orthopaedic surgeon with a full thickness rotator cuff tear will be eligible for study screening. The inclusion and exclusion criteria are listed below.

All eligible patients will receive information about the trial verbally and in writing. After signing written informed consent, they will be randomly allocated to undergo rotator cuff repair followed by standard of care structured rehabilitation with Oxandrolone administration or standard of care structured rehabilitation with placebo. Allocation will be performed using computer software and will occur at the pharmacy to ensure that all investigators are blinded. The USC Pharmacy will prepare sequentially numbered, opaque, sealed envelope containing the assigned interventions to ensure randomness is preserved. The surgeon, PI, study team, and physical therapist will not know to which study arm the patient was randomized. The protocol for rehabilitation will remain the same for all patients. The USC Pharmacy will provide the investigators with a list of all participants and group assigned at the end of the study. Investigators will not have access to the study group assignment for any participant during data collection, to ensure adequate double-blinding of both the investigators and participants.

Inclusion criteria

- Men and women age 40-75 years old who have failed nonoperative management of chronic, full thickness rotator cuff tears confirmed by MRI without contrast

Exclusion criteria

- Patients with prior shoulder surgery or prior rotator cuff repair
- Tears larger than 5cm
- Significant glenohumeral arthritis (Hamada Grade 2 or higher)
- Untreated diabetes mellitus
- Pituitary tumor
- Rheumatoid Arthritis
- Uncontrolled hypertension
- Congestive Heart Failure
- Myocardial Infarction within the past 6 months

- End-stage renal disease
- Liver enzymes two times the normal value
- DVT within the past 6 months
- Disorder of the coagulation system
- Currently taking anticoagulation
- Claustrophobia
- Prior or current use of anabolic steroids
- Chromosomal disorders
- Prostate cancer
- Breast cancer
- Hypercalcemia
- Medications that interfere with testosterone production or function, including but not limited to 5 α -reductase inhibitors

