6.0 Study Agent Administration and Safety

Oxandrolone Administration

Oxandrolone will be given to experimental men (12 mg BID) and women (6 mg BID) for 12 weeks starting the day of surgery. Previous clinical studies where oxandrolone was given for greater than 6 months have shown no androgenic effects, behavioral changes, sepsis, hirsutism, or acne in the patient population. Elevated liver transaminase levels have been noted but have been transient and asymptomatic.¹⁻³

Patient Safety and Compliance

Patients will have liver transaminase levels measured when preoperative labs are obtained. Additionally, liver enzymes will be assessed at 2, 6, 12, and 24 weeks after rotator cuff repair. Testosterone levels and a quantitative assay for oxandrolone will also be drawn prior to supplementation, at the 2 week post-operative visit and at the 6 month post-operative visit to assess for compliance. Any adverse medication reaction will be met with cessation of medication, but will continue to be followed for outcome data collection.

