10.0 Statistical Considerations

Statistical Methods

Descriptive statistics will be performed for participant demographics, historical information, intraoperative variables, as well as baseline testosterone, MRI measures of rotator cuff integrity, rotator cuff fatty infiltrate, rotator cuff muscle volume, shoulder strength, shoulder range of motion, patient-rated outcomes and body composition. Comparison for the primary outcome measure of rotator cuff integrity between groups from baseline to 1 year (primary endpoint) will be performed using a repeated measures analysis of Generalized Estimating Equation (GEE), appropriate for ordinal data. The GEE will also be used to compare between groups over time for the secondary outcome of fatty infiltrate (ordinal data). For all other secondary outcome variables, we will also use GEE for linear regression (ordinal data) or mixed model (continuous data) with repeatedly measured outcomes. Significance level will be established as $p < 0.05$. Analyses will be performed using STATA 13 software (College Station, TX) or SPSS and in consultation with the Statistics Department at USC.

Power Analysis and Sample Size

A power analysis for a sample size estimation was performed to detect a difference of 1 Sugaya grade (1-5 grades) classification (primary outcome) between the experimental and control group using 3 repeated measurements (baseline, 12 week, and 6 months).¹⁴ The power analysis was based with 2-sided alpha = 0.05 and power of 80%, and assuming a correlation among the repeated measures of 0.7 and overall SD of 2, giving a minimum sample size of 104 participants (n=52 participants in each group). This corresponds to an ANOVA effect size of 0.28 (28% of variance in primary outcome explained by treatment effect), or alternatively a moderate Cohen's D effect size (group mean difference divided by SD) of 0.5. Oversampling by 10% to account for possible attrition yields a total of 116 participants with 58 per group.

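### Surgeon-decided removal for altered rehabilitation and undefined control for adherence both act after randomisation, and nothing restores analysis as randomised; any bias in the Sugaya comparison is probably small, and the fix is cheap

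*Combined protocol and SAP*

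**What the plan says.** Section 3.0 (Postoperative Rehabilitation) contains two rules. If the rehabilitation course is altered, the treating surgeon is told and "will determine if the alteration in course warrants removal from the study"; no criteria are given. Adherence is then judged from treatment logs: "Patients who do not meet 80% adherence to the standardized protocol will be considered non-compliant and controlled for in the data analysis". No method is named.

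Both rules apply after allocation. Section 5.0 gives the order: "After signing written informed consent, they will be randomly allocated to undergo rotator cuff repair followed by standard of care structured rehabilitation". Table 1 in section 7.0 places randomisation on the day of the procedure.

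Three other passages bear on the point:

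- Section 5.0 protects the decisions from knowledge of the arm: "The surgeon, PI, study team, and physical therapist will not know to which study arm the patient was randomized", and "The protocol for rehabilitation will remain the same for all patients".
- Section 6.0 deals with adverse medication reactions, which "will be met with cessation of medication, but will continue to be followed for outcome data collection".
- Section 10.0 analyses the primary outcome "using a repeated measures analysis of Generalized Estimating Equation (GEE), appropriate for ordinal data". It names no analysis population, covariates or rule for missing data. On losses it says only: "Oversampling by 10% to account for possible attrition yields a total of 116 participants with 58 per group".

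**The concern.** Randomisation makes the arms comparable in the patients who were randomised. Dropping patients because of something that happened later, or adjusting for it, can undo this when that later event is related to both treatment and healing. Altered rehabilitation and poor adherence are events of this kind.

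Two things are open. Removal may mean only that study procedures stop, or also that data already collected are discarded. If visits stop, later MRIs are never taken and no analysis can recover them. A patient removed after week 12 still contributes the 12-week MRI, but only if collected data are kept, which is not stated. Controlling for non-adherence most naturally means adjustment or stratification, but a supplementary analysis or even exclusion would also fit the words. Two analysts could follow section 3.0 and report different primary results.

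Section 6.0 shows that continued follow-up was considered for patients who stop the drug. The same is not said for patients whose rehabilitation changes.

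**Working it through.** **1. Does another section settle it?** Section 6.0 covers adverse medication reactions only. Section 10.0 names a model but not who enters it. Section 3.0 (Feasibility) makes a coordinator responsible for confirming that postoperative MRIs are done, but does not mention patients who have been removed. The gap stands in the text available.

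**2. The plan's sample size reproduces.** Inputs from section 10.0: difference 1 grade, SD 2, three measurements, correlation 0.7, two-sided alpha 0.05.

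- Variance factor for the mean of three measurements: (1 + 2 × 0.7)/3 = 0.80.
- Effective SD: 2 × √0.80 = 1.789. Standardised difference: 1/1.789 = 0.559. Half of this is 0.28, the plan's ANOVA effect size.
- Noncentrality: 0.559 × √(n/2). At n = 52 per arm it is 2.85, giving 80.6% power. At n = 51, power is 79.8%, so 52 per arm is confirmed.
- Attrition: 52/0.9 = 57.8, so 58 per arm and 116 in total, as stated.

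**3. Losses against the allowance.** The allowance is 58 − 52 = 6 per arm, shared by ordinary attrition and removals. On the same inputs:

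| Analysed per arm | 58 | 55 | 52 | 51 | 50 | 47 |
|---|---|---|---|---|---|---|
| Power, % | 84.7 | 82.8 | 80.6 | 79.8 | 79.0 | 76.5 |

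Power falls below 80% at the seventh loss per arm.

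**4. Adherence used as a covariate (all rates assumed).** There is no true effect and 52 patients per arm. Sugaya I to V are 15/25/20/20/20% in both arms. A latent factor drives adherence (log-odds 0.75 per SD = mild, 1.5 = strong) and has correlation r with healing. Adherence is 70% in one arm and 80% or 85% in the other. The model is linear on grade with an adherence term, with 20,000 simulated trials per cell (Monte Carlo error near 5%: √(0.05 × 0.95/20,000) = 0.15 points).

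| Driver | r | Bias in grades, 70/80 and 70/85 | Type I error %, 70/80 and 70/85 |
|---|---|---|---|
| mild | 0.3 | 0.023, 0.042 | 5.0, 5.2 |
| mild | 0.5 | 0.046, 0.066 | 5.5, 5.6 |
| strong | 0.3 | 0.044, 0.065 | 5.3, 5.4 |
| strong | 0.5 | 0.072, 0.111 | 6.0, 7.1 |
| strong | 0.7 | not tabulated | 6.5, 8.9 |

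Swapping the arms (80/70, strong, r = 0.5) reverses the sign: −0.071. Equal adherence (75/75) gives 5.2%. Averaging the 12-week and 6-month grades gives 5.0 to 7.4% for r up to 0.5, and at most 9.9% at r = 0.7. These models simplify the planned ordinal GEE.

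A second simulation used a continuous outcome with SD 2 and a latent factor explaining half the variance. It gave no bias when the event depended on treatment alone or healing alone. Moderate dependence on both (13% vs 22% affected) gave a shift of about 0.10 grade. Strong dependence (17% vs 33%) gave 0.23 after exclusion and 0.25 after adjustment.

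**5. Removal of patients whose repair fails (rates assumed).** Same grades, true odds ratio 1, 58 per arm. Types IV and V make up 40%, so patients removed = 58 × 0.40 × share removed. An odds ratio above 1 favours the drug.

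| Share of failures removed, control/drug | Patients per arm | Odds ratio | Type I error % (rank-sum) |
|---|---|---|---|
| 5/10% | 1.2/2.3 | 1.04 | 5.1 |
| 10/20% | 2.3/4.6 | 1.09 | 5.5 |
| 25/50% (extreme) | 5.8/11.6 | 1.30 | 11.1 |
| 30/30% | equal | 1.00 | 5.0 |

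Swapping the arms in the first two rows gives 0.96 and 0.92.

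**The case against.** Four points can be made for the plan.

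- **Blinding.** Surgeon, therapist and patient are blinded and rehabilitation is common to both arms, so nobody can remove patients by known allocation. That stands. It does not exclude selection through drug effects on recovery or tolerability.
- **No stated causal link.** Section 2.0 (Aim 2) ties healing to better motion and strength. No section says that the drug changes adherence or the chance of altered rehabilitation. That stands too, so the bias is a possibility and not a prediction.
- **Small harm.** In the moderate scenarios the shift is about a tenth of the planned difference or less. Error rates of 9 to 11% need a strong driver with r = 0.7, or removal of a quarter against half of all failures. This is correct and limits the weight of the point.
- **MRI completion is overseen.** The coordinator's duty helps with ordinary attrition but does not extend in words to removed patients.

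A reader might also infer that non-adherent patients are to be excluded and that the trial is then underpowered. Section 3.0 speaks of removal for one situation and of control in the analysis for the other, so exclusion is the less natural reading. On the plan's SD of 2, 52 completers with 85%, 75% or 70% adherent (assumed) would leave 44, 39 or 36 per arm and power of about 74%, 68% or 65%. But 2 is the largest population SD that a 1 to 5 scale allows. The grade distribution assumed in the bias work has SD √(11.15 − 3.05²) = 1.36, and power at those sizes is then 93 to 97%. The documents therefore do not support a claim that exclusion would leave the trial underpowered. Nor can the power loss be ranked against the bias: the two have no common scale, and the figures rest on different variances.

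**Conclusion.** The point holds and should be fixed, but its expected effect is usually small. What is certain is textual: two rules act after randomisation, one can end MRI follow-up, the other can condition the primary comparison on adherence, and no available section secures analysis as randomised.

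The consequence is conditional. Bias needs dependence on both treatment and healing. Under assumed moderate dependence, adherence adjustment costs about 0.02 to 0.11 grade and gives type I error of about 5 to 7%. Removal of about 1 to 5 failures per arm, differing between arms, gives 5.1 to 5.5%. Stronger assumptions give more. Without such dependence the bias is nil, and if the adherence analysis is supplementary, that rule leaves the primary result untouched. The direction cannot be told from the documents, so an inference that the plan favours the drug is not supported.

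The limit of 6 losses per arm rests on the plan's own inputs, including SD 2; with SD 1.36, power at 52 per arm would be 98.6%.

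**What to change.** Leave the surgeon's clinical decisions on rehabilitation untouched and change only follow-up and analysis.

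- **Section 3.0:** state that patients whose rehabilitation is altered continue scheduled MRI and outcome visits, subject to consent, and that data already collected are kept.
- **Section 10.0:** state that the primary analysis includes all randomised patients in their allocated group, with rehabilitation adherence neither a covariate nor an exclusion criterion.
- **Adherence:** replace the open wording with a named method (adherence-adjusted or adherent-only), used only in a labelled sensitivity analysis.
- **Reporting:** give adherence and rehabilitation alterations by arm.

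The cost is a few sentences, a few extra MRIs and visits, and slight dilution of the estimate by non-adherent patients. The sample size stays at 104, or 116 with attrition.
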